The effect of non-invasive auricular vagus nerve stimulation paired with rehabilitation on gait and balance impairments in chronic stroke: A randomised controlled feasibility trial.

Primary investigator: [name] **Primary Supervisor:** [name] **Co-Supervisors:** [name], and [name]. [name], [name]

Innovation, Implementation and Clinical Translation (IIMPACT) in Health, Allied Health and Human Performance, University of South Australia

Background

Stroke is a leading cause of disability in Australia, costing the economy \$6.2 billion of direct cost and \$26 billion of indirect cost from lost wellbeing and mortality in 2020 [1]. Recovery from stroke mainly occurs in the subacute stage, driven by a period of enhanced neuroplasticity [2]. However, a large proportion of stroke survivors endure long-term impairments including limb weakness, impaired mobility and balance [1]. Hence, there is an imminent need for novel treatments to enhance stroke recovery. Recently, promising studies have demonstrated that pairing invasive vagus nerve stimulation (iVNS) with rehabilitation can enhance motor function post-stroke. For example, a multicentred, triple-blind, randomized controlled trial that included 106 stroke survivors with upper limb weakness has shown that iVNS paired with repetitive task training (for 6 weeks, 3 x 1 hour weekly) led to greater upper limb recovery compared to sham treatment [3]. Interestingly, the improvement in the active group was two to three times higher than the sham group, and more importantly, this effect was preserved for 90 days after treatment. Following this study, iVNS received approval from the Food and Drug Administration (FDA) as adjuvant therapy for chronic stroke rehabilitation [4]. However, iVNS is costly and requires a surgical procedure, limiting accessibility and imposing potential safety risks including symptomatic bradycardia, localised infection, and transient vocal cord palsy [3, 5, 6].

Transauricular vagus nerves stimulation (taVNS) has been used successfully as a non-invasive, and potentially, safer alternative to iVNS as an adjuvant therapy for drug-resistant epilepsy and major depression [7, 8]. Recently, taVNS paired with rehabilitation was found to be a feasible and safe approach to improve upper-limb weakness in subacute [9] and chronic [6, 10] stroke. The first-in-human pilot study investigating taVNS to enhance upper-limb recovery in 14 adults with chronic stroke was conducted in 2017, showing that taVNS paired with robot-assisted rehabilitation was safe and feasible with effects in favour of the active compared to the sham group [6]. Similar results were observed in subacute stage of ischaemic stroke where taVNS paired with conventional rehabilitation improved upper-limb weakness in 21 people who received 30 minutes of taVNS followed by 30 minutes of conventional therapy for 15 consecutive days [9]. More importantly, the effect of taVNS was preserved 10 weeks from the end of the intervention. Although these early taVNS studies in stroke shared some key limitations, including small sample size, the use of different stimulation parameters, and different sham protocols, their promising results, along with the good quality evidence for iVNS in stroke recovery, warrants further exploration of taVNS role in enhancing stroke recovery.

Altered gait and balance dysfunction are two common stroke-related deficits. Gait dysfunction occurs in more than 80% of people with stroke [11]. This leads to difficulty with mobility and performing activities of daily living [12]. Impaired balance is also common after stroke with 70% of people reporting a fall within 1 year of their stroke [11]. The positive effect of taVNS on upper-limb motor function, likely driven by enhanced neuroplasticity [13, 14], suggests that pairing taVNS with other therapies might prove beneficial. However, the effect of taVNS combined with gait/balance training to enhance recovery of the lower limb has not been studied. This research aims to assess the feasibility, safety, and preliminary efficacy of taVNS

paired with rehabilitation for enhancing gait and balance impairments in people with chronic stroke (> 6 months).

Method:

Aim: The primary aim is to assess the feasibility and safety of taVNS to enhance gait and balance impairments in people with chronic stroke. The secondary aim is to gain preliminary data about the efficacy of taVNS in this population.

Study Design: This will be a randomised double-blinded sham-control trial. Participants will be assessed at baseline, immediately post, and at \geq 30 days after completing the intervention.

Participants:

Participants will be recruited from the UniSA Health and Medical Clinic as well as advertising at Stroke SA, Stroke Foundation and via social media. All assessments and treatments will be conducted within the UniSA Health and Medical Clinic at the City West.

Power and sample size: A power calculation is not necessary for a feasibility study; further no studies have investigated the use of taVNS for enhancing gait and balance. However, to provide some insight, we have performed a power calculation based on effect sizes obtained from a previous upper limb taVNS study [10]. It was determined that 18 participants will be required (in each group) to detect a moderate effect size of 0.70, given an alpha level of 0.05 and power of 80 % [15].

Inclusion criteria: Aged 18 years or older; first-ever haemorrhagic or ischaemic stroke at least 6 months earlier; can walk 10 meters with or without a gait aid and with or without assistance (assessed using 10-meter walk test [16]), no history of other neurological conditions; gait and/or balance impairment; ability to give informed consent and to understand instruction.

Exclusion criteria: Previous vagus nerve surgery; cognitive impairment and/or language impairment that might impact the person's ability to consent or understand instructions (MOCA score of less than 18); severe pain in any joints of the affected limb; advanced cardiac, pulmonary, kidney or liver condition; pregnancy; use of neuroactive medication [6]; active implants; cerebral shunts; open skin at the point of stimulation.

Intervention: The physical rehabilitation therapy component of the intervention will be tailored to participants' impairments and goals. It will consist of 15 sessions conducted over 6 weeks (2-3 x 1-hour sessions per week). Concurrently with the physical rehabilitation, participants will receive one of taVNS conditions (active or sham, allocation will be randomised).

taVNS stimulation parameters:

The stimulation will be provided using the tVNS[®] R device (tVNS Technologies GmbH, Reichenschwand, Germany). Stimulation intensity will be individually adjusted to a level that is above the individual's sensory threshold and below pain threshold (tolerable stimulus). A pulse width of 0.3 ms, a frequency of 25 Hz, and a pulse pause ratio of 30 sec on: 30 sec off will be used. The electrode will be placed at left ear, specifically at cymba concha. Participants will not be aware of the stimulation condition they are receiving for the duration of the treatment.

Randomisation, blinding, and concealment:

Participants will be assigned a number from 1 to 40 and allocation to intervention (active or sham taVNS) will be randomised (1: 1 ratio). Randomisation will be completed using the web application available at https://www.randomizer.org/. Subjects will be enrolled in consecutive order.

All participants will not be aware of the stimulation condition they are receiving for the duration of treatment. The sensory and pain threshold for taVNS stimulation will be measured for all participants in the first assessment session (baseline measures) and participants will be familiarised with the taVNS device. Prior to randomisation, all participants will be told that" In this study, we will use different stimulation parameters for different groups of participants. Depending on the parameters used in the group that you will be assigned to, you may feel the stimulus, normally a tingling/prickling/stinging/warmth/vibration sensation at the stimulation site, or feel nothing at all".

The physiotherapist who will provide the intervention will receive a sealed randomisation envelope imprinted with participants' numbers and will provide the appropriate intervention as indicated. The outcome assessor will be blinded.

Outcome Measures: A variety of outcome measures will be used throughout this study as follows:

1. Feasibility: This will be determined by measuring compliance to intervention, adverse events, patient satisfaction, and effectiveness of blinding using criteria described in table 1.

	Proceed	Proceed with Protocol	Significant Amendments Required
		Amendments	
	50% of eligible participants	40% of eligible participants	25% of eligible participants consent to participate
Criteria	consent to participate	consent to participate	
	60% of participants complete	40% of participants complete	25% of participants complete the intervention
	all the sessions of the	the intervention protocol	protocol
	intervention protocol		
	50% found intervention useful	25% found intervention useful	$< 25\%$ found intervention useful (Likert $\ge 4/5$)
	$(Likert \ge 4/5) [17]$	$(\text{Likert} \ge 4/5)$	
	50% found intervention helpful	25% found intervention helpful	$< 25\%$ found intervention helpful (Likert $\ge 4/5$)
	$(\text{Likert} \ge 4/5)$	$(\text{Likert} \ge 4/5)$	
	50% found intervention	25% found intervention	< 25% found intervention delivery acceptable
	delivery acceptable (Likert \geq	delivery acceptable (Likert \geq	(Likert $\geq 4/5$)
	4/5)	4/5)	
	Blinding \geq 90% (Assessed	Blinding $\geq 50\%$	Blinding < 50%
	using a blinding questionnaire		
	that we developed, see		

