	appendix 1)		
	Moderate to severe adverse	Moderate to severe adverse	Moderate to severe adverse events occur in \geq 50 of
	events occur in < 20 % of	events occur in $\ge 20\%$ of	participants.
	participants	participants.	

Table 1: Feasibility and Acceptability Criteria

1. Safety: We developed a safety questionnaire and it will be used to assess adverse events at the end of each week (see appendix 1). Participants will also be asked to report any AEs that occurs during any of the session immediately to the physiotherapist delivering the intervention. The AEs questionnaire was developed based on findings from a scoping review that our team has conducted recently (data has been synthesised but has not been published yet) and guided by a systematic review reporting on safety of non-invasive taVNS [10].

2. Efficacy: Preliminary efficacy will be assessed using outcome measures described in table 2. These outcome measures were chosen following recommendations in current stroke literature regarding standardised sensorimotor measurements in stroke recovery trials [16]. Measurements will be conducted at 3-time points (baseline, post-treatment, and 30 days follow-up)

Efficacy outcomes	Outcome measure
Walking 1. Speed 2. Endurance 3. Gaitrite	10-meter walk test (10MWT) 6-minutes walk test (6MWT) Spatial and temporal parameters of gait
Balance Global Disability Self-efficacy	Brief BESTest [18] Modified Rankin Score (mRS) [19] Stroke Self-Efficacy Scale (SSES) [20].

3. Participants experience with taVNS

Qualitative data will be obtained using a structured interview which will be conducted for each participant after 5 days of the final treatment session provided, using attached interview guide (see Appendix 2).

Statistical analysis: The feasibility will be reported against the criteria in table 1. For efficacy outcomes, a linear mixed model analysis will be used to compare two groups (active and sham) and 3-time points (baseline, post-intervention, and follow-up). Safety outcomes will be summarised descriptively. Qualitative interviews will be analysed and reported using thematic analysis. The effectiveness of the sham method in blinding participants will be assessed using a blinding questionnaire which was developed based on the work of Bang et al. (2010) [21] (see Appendix 3) that we developed, and results will be summarised descriptively.

References

- 1. Economics, D.A., *The economic impact of stroke in Australia*. 2020.

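### The stated 80% power at 18 per group for an effect size of 0.70 does not follow from the stated inputs for an active-versus-sham comparison: an unadjusted two-group test has about 53%

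*Protocol*

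**What the plan says.** The Power and sample size paragraph of the protocol (Method, Participants) first says that a feasibility study does not need a power calculation, then offers one for insight. Its effect size is taken from an earlier study of the same stimulation in the upper limb. The result reads: "It was determined that 18 participants will be required (in each group) to detect a moderate effect size of 0.70". The significance level is set at 0.05 and the power at 80%. A reference to the G*Power program is attached. The paragraph does not name the test, its sidedness, the effect-size index or any within-person correlation.

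Two other places fix the comparison that this number has to serve. The section Randomisation, blinding, and concealment states: "Participants will be assigned a number from 1 to 40 and allocation to intervention (active or sham taVNS) will be randomised". Allocation is 1:1, which makes 20 per arm. Under Statistical analysis, the plan for efficacy reads: "a linear mixed model analysis will be used to compare two groups (active and sham) and 3-time points (baseline, post-intervention, and follow-up".

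**The concern.** Because the number is given per group in a two-arm trial, a reader will take it as the sample size for active versus sham. On the stated inputs it is far too small for the ordinary two-group test. The unstated sidedness does not close the gap, and neither do the two further participants per arm implied by 40 numbers.

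This is the only numerical basis given for the trial's size. Two readers could be misled. One sees an efficacy difference that is not significant and, trusting 80% power, counts it as fair evidence against an effect of 0.70; under the unadjusted test such an effect would be missed about 47% of the time (1 − 0.53). The other plans the next trial by the same route and arrives at roughly half the number an unadjusted comparison needs (18 against 34).

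**Working it through.** **Inputs.** From the protocol: 18 per group; effect size 0.70; alpha 0.05; power 80%; 1:1 allocation; 40 numbers, so 20 per group. Assumed: 0.70 is a standardised mean difference d (SD of one visit), and the test is two-sided, with one-sided shown as well.

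**1. The plan's figure as an unadjusted two-group test.** Power is the probability that a noncentral t variable, with 2n − 2 degrees of freedom and noncentrality d√(n/2), passes the critical value.
- n = 18: noncentrality 0.70 × √9 = 2.10; 34 df; two-sided critical value 2.032.
- n = 20: noncentrality 0.70 × √10 = 2.21; 38 df; critical value 2.024.

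| | Two-sided | One-sided |
|---|---|---|
| Power, 18 per group | 53.2% | 66.0% |
| Power, 20 per group | 57.8% | 70.2% |
| n per group for 80% | 34 | 26 |

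The stated 18 is not reproduced. Solving for d at 80% power, two-sided, gives 0.961 at 18 per group and 0.909 at 20.

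**2. What would bring 18 per group to 80%.** The effective d must rise from 0.70 to 0.961, so the residual variance must fall to (0.70/0.961)² = 0.53 of its unadjusted value.
- *One post-treatment visit, baseline-adjusted.* Residual variance is 1 − r², where r is the baseline-to-post correlation. Setting 1 − r² = 0.53 gives r ≈ 0.69. At lower values, power with 18 per group is 57% (r = 0.3), 65% (0.5) and 72% (0.6).
- *Change from baseline at one visit.* Variance is 2(1 − r). Setting this to 0.53 gives r ≈ 0.73.
- *Average of both post-treatment visits, baseline-adjusted,* assuming the same correlation r between every pair of visits and the same effect at both. Residual variance is (1 + r)/2 − r². At r = 0.43 it is 0.715 − 0.185 = 0.530, so power is 80%. It is 82% at r = 0.5. Below 0.43 it dips only slightly: the variance peaks at r = 0.25 (0.625 − 0.0625 = 0.5625), where d is 0.70/0.75 = 0.933 and power 77.6%; it is back at 80% for r below about 0.07. At 20 per group it stays at or above 82%.
- *The same average with unequal correlations.* If the two post-treatment visits correlate at s, the variance is (1 + s)/2 − r². For illustration, r = 0.5 and s = 0.8 give 0.90 − 0.25 = 0.65, d = 0.868 and power 72% at 18 per group.

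**3. Where 18 might come from.**
- One-sample or paired t-test, two-sided: noncentrality 0.70 × √18 = 2.97 on 17 df gives 79.9%. A strict search for at least 80% returns 19 (82.3%).
- Repeated-measures ANOVA, between-group factor, f = 0.35 (d/2), three visits, correlation 0.3, 36 in total: noncentrality 0.35² × 36 × 3/(1 + 2 × 0.3) = 8.27 on 1 and 34 df gives 79.8%.
- The same ANOVA with two visits and correlation 0 first passes 80% at 36 in total.
- If 0.70 were the index f (equal to d = 1.4), 18 in total gives 79.6%, but the protocol says 18 in each group.

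Several routes land near 18, so the number alone does not identify the method.

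**The case against.** The strongest defence is that the planned analysis is not a single-visit t-test. It is a mixed model over baseline and two later visits, and such a model can yield a more precise contrast. This stands in part. Under the equal-correlation assumption, a baseline-adjusted average of both later visits puts 18 per group close to 80% at any correlation, so 53% should not be presented as the power of every analysis the model could give. It does not rescue the sentence. The protocol does not name that contrast, does not state a correlation, and does not say that the effect is expected to be equal at both visits. The gain also shrinks if the two later visits correlate more strongly with each other than with baseline.

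A second defence is that a feasibility trial needs no power calculation. The protocol says so itself; feasibility and safety are the primary aim, and Table 1, which governs progression, contains no efficacy criterion. This limits the weight of the point, but a figure that has been stated should still follow from its inputs.

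Three stronger readings are tempting and not supported:
- A reader might infer that a paired-test sample size was relabelled as per group. The near match at 79.9% makes this possible, but other routes fit as well and a strict search would have returned 19.
- A reader might infer that the 40 is 36 plus an allowance for loss. The protocol never says so.
- A reader might infer that the trial must be enlarged. Nothing in its aims or progression criteria depends on 80% power for efficacy.

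**Conclusion.** The point holds as a moderate correction. The 80% claim is not supported by the inputs beside it for the active-versus-sham comparison: as an unadjusted two-group test, 18 per group falls short by about 27 percentage points two-sided (80 − 53) or 14 one-sided (80 − 66). The sizes rest on reading 0.70 as a standardised mean difference and, for 53%, on a two-sided test. A design with about 80% power at 18 per group exists, but only through baseline adjustment or repeated measures that the protocol leaves unstated. It is therefore fair to say that the figure is unsupported as written, and not fair to say that no analysis of this trial could reach it.

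**What to change.** Leave enrolment as it is and replace the power sentence in one of three ways.

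1. State that the trial is sized for feasibility and give what that size delivers. Possible wording: *The sample size is set for feasibility. For an unadjusted two-sided comparison of two groups at alpha 0.05, 18 (20) per group gives 53% (58%) power for a standardised difference of 0.70, and 80% power for a difference of 0.96 (0.91).*
2. If a more precise contrast was intended, name the test, contrast, sidedness, effect-size index and assumed correlation or correlations that lead to 18 per group.
3. Drop the 80% claim.

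Whichever is chosen, say how the 18 per group relates to the 40 numbers allocated. The cost is one sentence, and under the first option the stated power becomes less favourable. Procedures, visits and enrolment do not change.

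### Table 1's consent and completion rows do not form contiguous bands, so some feasibility results get no verdict on any reading, and completion is worded differently between columns

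*Protocol*

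**What the plan says.** Under Method, Aim, the Protocol states: "The primary aim is to assess the feasibility and safety of taVNS". Under Statistical analysis it adds: "The feasibility will be reported against the criteria in table 1". Table 1 (Outcome Measures, item 1) has three columns: proceed, proceed with protocol amendments, and significant amendments required.

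- **Consent:** 50% / 40% / 25% of eligible participants. The third cell reads "25% of eligible participants consent to participate".
- **Completion:** 60% / 40% / 25%. The third cell begins "25% of participants complete the intervention". The first cell specifies "all the sessions of the" intervention protocol; the second and third refer to the intervention protocol without mentioning sessions.
- **Useful, helpful and acceptable (Likert rows):** 50% / 25% / < 25%.
- **Blinding:** ≥ 90% / ≥ 50% / < 50%.
- **Moderate to severe adverse events:** < 20% / ≥ 20% / a third cell reading "Moderate to severe adverse events occur in \geq 50 of" participants.

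The planned number comes from Randomisation, blinding, and concealment: "Participants will be assigned a number from 1 to 40". The intervention is 15 sessions over 6 weeks. The Protocol gives no rule for results that fall between or below the printed percentages.

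**The concern.** A progression table should assign every possible result to exactly one column. The Likert rows do this once their first two figures are read as minimums, because the third column starts where the second stops. The blinding row does it explicitly. The consent and completion rows do not: their third figure, 25%, does not adjoin the second, 40%, and no sign shows whether it is a floor, a ceiling or a point.

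Because feasibility is judged against this table, a result in the unclassified zone would leave the primary conclusion to be settled after the data are known. The change of wording for completion adds a second uncertainty, since the three columns may not be banding the same quantity. These thresholds are fixed in the Protocol itself, so this is a stated rule that does not work, not a detail left for an analysis plan.

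**Working it through.** There is no published calculation to reproduce, so the check is an enumeration.

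**Inputs.** N = 40 (Randomisation section), taken as the denominator for completion. Completion cut-offs are 60%, 40% and 25% of 40, that is 24, 16 and 10 participants. The Protocol states no expected completion rate, so the true rate p is assumed and shown over a range.

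**Step 1: which counts get no column.**

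- *First two figures as minimums, third as 25% or less:* the columns are ≥ 24, 16–23 and ≤ 10. Counts 11–15 (27.5% to 37.5%) are unclassified. If the third means < 25%, as in the Likert rows, 10 joins them and the gap is 10–15.
- *All three figures as minimums:* the columns are ≥ 24, 16–23 and 10–15. Counts 0–9 (below 25%) are unclassified.
- *Figures as exact points:* only 10, 16 and 24 completers match any column.

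No reading covers 0 to 40.

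**Step 2: chance of landing in the gap.** X ~ Binomial(40, p).

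| Assumed p | P(11 ≤ X ≤ 15), third column as 25% or less | P(X ≤ 9), all minimums |
|---|---|---|
| 0.30 | 0.576 | 0.196 |
| 0.35 | 0.573 | 0.064 |
| 0.40 | 0.405 | 0.016 |
| 0.50 | 0.076 | 0.0003 |
| 0.60 | 0.003 | < 0.0001 |

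**Step 3: consent.** The number of eligible people is not given, so no probability is attached. The same hole exists. If 40 consent, the rate is 40% with 40/0.40 = 100 eligible and 25% with 40/0.25 = 160. On the first reading, more than 100 but fewer than 160 eligible gives no verdict; on the all-minimums reading, more than 160 gives none.

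**Step 4: the completion wording.** As an illustration, suppose 8 of 40 attend all 15 sessions and 20 more attend 14. Counting only full attendance gives 8/40 = 20%, below every figure in the row. A definition that accepts 14 gives 28/40 = 70%, above the figure for proceeding. The table does not say which measure columns two and three use.

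**The case against.** The strongest reply is that these are descriptive progression criteria. No test, error rate or participant protection depends on them, and a very low result would in practice be read as the worst column. That stands as an argument about severity. It does not make the rule complete, because the table does not state that convention.

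Four stronger readings are tempting and are not supported.

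- *A reader might infer that 25% to 40% never receives a decision.* That depends on the third column meaning 25% or less (or < 25%, or exactly 25%). If 25% is a minimum, results from 25% to below 40% fall in the third column, and the hole lies below 25%.
- *A reader might infer that an undefined verdict is likely.* It is likely only if true completion is poor, and the Protocol gives no expected rate. On either reading the chance is at most about 8% at a true rate of 50% and 0.3% at 60%.
- *A reader might infer that the adverse-event row gives contradictory verdicts or sets an unreachable count.* The uncapped middle band is a nested ladder, like the blinding row, in which the more severe column would naturally govern. The other cells of that row are percentages, so the missing percent sign is clerical or a product of text extraction.
- *A reader might infer that requiring every session makes proceeding unattainable.* That would criticise how strict a threshold is, not a gap in the bands, and the Protocol gives no attendance figures from which to judge it.

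On the completion wording, the later cells may simply be shorthand for the first. That is plausible, but the text does not say so.

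**Conclusion.** The point holds, at moderate severity. The consent and completion rows of the primary decision table leave some results unclassified on every reading examined, in contrast to the Likert and blinding rows beside them. Which results are affected depends on an unstated sign: 11–15 of 40 completers (10–15 if the third column means < 25%), or 0–9 of 40. The probabilities rest on 40 participants as the denominator, a binomial model and assumed true rates. They matter mainly when completion is low, which is when the rule is most needed. The completion measure may also differ between the first column and the other two. The adverse-event row needs tidying only and carries no weight in this conclusion.

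**What to change.** Before results are seen, restate both rows as exhaustive and mutually exclusive bands, by one of two routes.

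- **Boundary at 40%.** Consent ≥ 50% / 40% to < 50% / < 40%; completion ≥ 60% / 40% to < 60% / < 40%. For 40 participants, completion becomes ≥ 24 / 16–23 / ≤ 15.
- **Boundary at 25%, as in the Likert rows.** Consent ≥ 50% / 25% to < 50% / < 25%; completion ≥ 60% / 25% to < 60% / < 25%. For 40 participants, completion becomes ≥ 24 / 10–23 / ≤ 9.

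The two routes give different verdicts for 10–15 completers, so the sponsor must choose and record one. Use a single definition of completion in all three columns, stated in terms of the 15 sessions.

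As a minor tidy-up, end the middle adverse-event band where the third begins, and confirm that the 50 there is a percentage.

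The cost is a change of protocol wording; no design, sample size or data collection changes.
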